## INTRODUCTION & RATIONALE

Scleral lens (SL) prescribing has dramatically increased over the past few years likely because of the advent of better SL designs, better materials, and greater awareness of the technology. SL market growth has also likely increased because SLs were once reserved for patients with complex ocular surface diseases, though advances with SL technologies have allowed SL fitting to include patients with dry eye and even patients who have relatively uncomplicated refractive errors. While SLs are maintained and cared for much like soft contact lenses (e.g., they require a contact lens care system), SL wearers also need help with applying their lenses. Patients specifically are advised by their care provider to insert their SLs with their fingers (tripod method), a DMV inserter with an open or closed end (hole potentially aides in vision), or a specialized o-ring that is balanced on a finger. Our clinic also utilizes a tea light candle with a DMV inserter attached to the top of it when patients have mobility issues. While work from this investigator's study group has found that 54% of patients prefer DMV inserters for applying their SLs as compared to the above other options, these preliminary data were obtained through a cross-sectional electronic survey from subjects who completed their SL fitting up to two years ago. Therefore, the goal of this proposal is to conduct a randomized controlled study aimed at learning the best method for applying SLs and factors associated with successfully completing SL application and removal training. These data are needed because it will help practitioners with patient education and because it may increase the likelihood that patients will be successful with SLs.

## SPECIFIC AIMS

This study will address the following specific aims and associated hypotheses:

- 1. Determine a neophyte SL wearers' preferred scleral lens application method.** *Hypothesis 1: There will be no statistical difference in the SL patient's preference among the five application methods (DMV inserter with an open or closed end, three fingers, o-ring, tea light candle) after the initial training visit.*
- 2. Determine factors that influence the amount of time it takes for a neophyte SL wearer to be able to successfully apply and remove their SLs.** *Hypothesis 2: Past contact lens experience, SL diameter, uncorrected visual acuity, and subject age will all influence the total time needed to complete all five application methods successfully.*

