**4. Randomization:** The investigator will access the online randomization tool (REDCap) and determine the order by which subjects will apply their lenses (*DMV inserter with an open end (A), DMV inserter with a closed end (B), three fingers (C), o-ring (D), tea light candle (E)*). Right eyes will undergo the application protocol; however, if the patient only needs a SL for their left eye, the left eye will undergo the protocol. Hand and eye dominance will be recorded. Subjects will then be instructed via training videos created by the investigators on how to do each application method. Each training video will be shown before starting each application method, and the examiner will answer the subject's questions prior to attempting the application method. The same investigator will teach each subject. Subjects will be timed during each application; however, time recording will not be made obvious. After a subject successfully completes an application method once for the designated eye, they will be asked to do the subsequent method. If a subject is unsuccessful with a method and declines to continue that method after being encouraged, the time will be recorded, and they will be allowed to try the next method. The subject will be allowed up to 15 minutes to complete each method. If the subject is unable to complete the method within that time frame, they will be instructed to do the next method to help avoid fatigue. If a patient stops a procedure before completing an application, this event will be recorded. Patients will be encouraged to try all five methods on the same day; however, subjects will be allowed to come back on a subsequent day if they get tired. Subjects will be asked to rank the ease of application for each method from easiest to most challenging after trying each method. If a subject needs a SL for their contralateral eye, they will be taught how to apply this lens after they have completed the training for their designated eye. If a subject is able to apply the lenses, they will be asked to remove the lenses as well. Only one removal method will be used (small plunger), and the removal time will also be timed for each method (timed separately from application).

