**5. SL Release:** After a subject completes the application and removal process, they will be given everything they need to wear the lenses (non-preserved saline (Adipack), application devices). They will also be given a trial bottle of Boston Simplus (contact lens care system), and they will be allowed to try their lenses for about one week. Subjects will be instructed to use their preferred application method at home.

**6. SL Adaptation Form:** Subjects will be given a take-home diary to complete during the one-week trial period. This diary will ask the subject about their experience with applying and removing their lenses, their comfort, and their perception of the SLs.

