#### *Visit 3: Outcome Visit*

**1. Visual Acuity:** Visual acuity with SLs will be measured with a high-contrast Snellen chart. If the patient is unable to read the 20/40 letters, the investigator will pinhole over the patient's unaided or presenting refractive error correction to determine the subject's visual potential.

**2. SL Evaluation:** The investigator will use a slit-lamp biomicroscope to evaluate the SLs. The subject will be required to have worn their lenses for at least two hours before the study visit. Anterior segment optical coherence tomography (OCT) will also be performed to obtain an accurate central corneal clearance measurement.

**3. Questionnaires:** All subjects will be asked to complete the SPEED, CLDEQ-8, and OCL-QoL questionnaires at the final SL fitting visit. They will also be asked to complete an investigator-designed questionnaire to understand the initial SL wearing experience.

**4. Study Completion:** The subject will be compensated, and the subject will be exited from the study, but they will be encouraged to continue their SL care with their provider.

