#### Data Collection and Analysis

Data collection will be performed with Research Electronic Data Capture (REDCap). Data will be analyzed with STATA 16 (StataCorp LLC; College Station, TX). Means and standard deviations will be used to understand general data trends. ANOVA will be used when comparing application methods. Regression analysis will be used to find associations with the speed of being able to complete the application process. Paired t-tests will be used to compare questionnaire scores at the final visit to the baseline visit. If the assumptions of these tests cannot be met, suitable alternative statistical tests (e.g., Kruskal-Wallis) will be used.

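### Aim 1 asks which method subjects prefer after training, but Visit 2 specifies only an ease ranking, and the five-method comparison is not stated to be within-subject

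*Combined protocol and SAP*

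**What the plan says.** **The aim.** Under Specific Aims, Aim 1 is to find the application method that first-time scleral lens wearers prefer. Hypothesis 1 states: "There will be no statistical difference in the SL patient's preference among the five application methods", and sets the time as the end of initial training.

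**What Visit 2 collects.** Step 4 randomizes the order of the five methods and takes each subject through them in turn: "After a subject successfully completes an application method once for the designated eye, they will be asked to do the subsequent method". It also says "Subjects will be timed during each application". Removal times and attempts stopped early are recorded too. The subject's own comparison of the methods is to "rank the ease of application for each method from easiest to most challenging". Step 5 then says "Subjects will be instructed to use their preferred application method at home". Step 6 adds a take-home diary: "This diary will ask the subject about their experience with applying and removing their lenses".

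**What Visit 3 collects.** Step 3 includes an "investigator-designed questionnaire to understand the initial SL wearing experience".

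**The analysis.** Data Collection and Analysis says "ANOVA will be used when comparing application methods". It names paired t-tests for the questionnaire scores, and gives Kruskal-Wallis as an example of what to use if the assumptions of the listed tests fail.

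**The concern.** There are two gaps, and both bear on the main question of the study.

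1. **Outcome.** The aim is about preference and the scheduled rating is about ease. The two can differ: a method may be easy in the clinic yet not be the one a subject would choose. The protocol does not define the easiest method as the preferred one. Any preference item in the diary or the Visit 3 questionnaire would be answered during or after home use, which is later than Hypothesis 1 specifies. By then subjects have been directed to their preferred method, so experience of the five is no longer balanced.

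2. **Test.** All five measurements come from the same subject. Pairing is specified for the questionnaires but not for the comparison of methods, and the one named fallback assumes independent groups. Ranks are ordinal and times stop at a 15-minute limit, so the fallback may well be needed.

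At stake is whether Aim 1 is answered by the intended measure, and whether the chosen test keeps its stated error rate.

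**Working it through.** The plan states no significance level, power or effect size for comparing methods, so there is no figure of its own to reproduce here. An alpha of 0.05 is assumed throughout.

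**A. Outcome, stage by stage**

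| Stage | Subject-rated comparison of methods in the text | At the time Hypothesis 1 names? |
|---|---|---|
| Visit 2, step 4 | Ranking of ease | Yes |
| Visit 2, step 5 | Preferred method assumed; no recording step | Yes |
| Visit 2, step 6 (diary) | None named; covers experience, comfort and perception | No, home use |
| Visit 3, step 3 | None named; covers the early wearing experience | No, after home use |

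No row has a stated preference record at the right time.

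**B. Independent-groups tests on ranks**

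Inputs: n = 25 subjects (Subjects and Recruitment) and k = 5 methods (Visit 2, step 4). Complete, untied rankings are assumed.

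For such data the Kruskal-Wallis statistic H is a fixed multiple of the Friedman statistic Q:

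H = [(nk − 1) / (n(k − 1))] × Q = (124 / 100) × Q = 1.24 Q.

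With no true difference, Q is approximately chi-square on 4 degrees of freedom, with 5% critical value 9.488. Kruskal-Wallis therefore rejects when Q exceeds 9.488 / 1.24 = 7.65, and P(chi-square on 4 df > 7.65) = 0.105.

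Simulation of 40,000 trials with no true difference, n = 25:

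| Test | False-positive rate |
|---|---|
| Kruskal-Wallis | 10.1% |
| One-way ANOVA | 10.7% |
| Friedman | 4.7% |
| Repeated-measures ANOVA | 5.1% |

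Example with rank sums 60, 68, 75, 82, 90 (total 375 = 25 × 15):

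- Sum of squares: 3,600 + 4,624 + 5,625 + 6,724 + 8,100 = 28,673.
- Q = [12 / (25 × 5 × 6)] × 28,673 − 3 × 25 × 6 = 458.768 − 450 = 8.768, p = 0.067.
- H = 1.24 × 8.768 = 10.872, p = 0.028.

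The same data are significant by one test and not by the other.

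**C. Independent-groups tests on times**

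Assumptions, none from the plan except the 15-minute limit: log-normal times, median 4 minutes, log SD 0.6, capped at 15 minutes, one method 30% faster. There were 10,000 simulated trials per setting.

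| Within-subject correlation | Kruskal-Wallis power | Friedman power |
|---|---|---|
| 0.3 | 40% | 55% |
| 0.5 | 35% | 73% |
| 0.7 | 27% | 92% |

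With no true difference, Kruskal-Wallis rejects in 1.0%, 0.1% and 0.0% of trials at these correlations, and Friedman in 4.2% to 4.9%. One-way ANOVA also loses power relative to repeated-measures ANOVA. The size of that loss depends on whether times are analysed in minutes or logs, which the plan does not say, so no figure is given.

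The directions differ because ranks within a subject are negatively correlated (their sum is fixed), whereas times within a subject are likely to be positively correlated.

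**The case against.** **Preference may well be captured.** The instruction at lens release makes sense only if a preferred method has been identified by then, and the REDCap forms, diary and Visit 3 questionnaire are not reproduced. For first-time users, ease might also be the intended measure of preference. This stands in part. A reader might infer that preference is never collected; the documents do not support that. They show only that no step says where it is recorded at the time Hypothesis 1 names, and that ease is not defined as its measure.

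**The plan does not commit to a wrong test.** ANOVA includes its repeated-measures form, Kruskal-Wallis is one example covering several analyses, and any alternative has to be suitable. This also stands. A reader might infer that an independent-groups analysis will be run; the text leaves it open. The figures above are therefore conditional.

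**Visit 2 is richer than an ease ranking, and home use is not confined to one method.** Both are correct. Times and stopped attempts are recorded as well, though neither is a preference. Subjects are directed to their preferred method but not told to use it exclusively, and more than one device is handed out. Experience of the methods becomes unequal, not necessarily limited to one.

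**Times are secondary.** No hypothesis compares times between methods; Hypothesis 2 concerns total time, analysed by regression. The power figures rest on assumed values, and few simulated times reach the cap, so failed and abandoned attempts are barely represented. They show direction and rough size only.

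**The study is preliminary.** That may excuse a small sample. It does not explain leaving the main outcome or its test unspecified.

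**Conclusion.** The point holds as a gap in specification. The protocol sets preference after training as the Aim 1 outcome, specifies only an ease ranking as the subject-rated comparison at that visit, and does not state a within-subject test for data that are within-subject by design.

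The rank result is the firmest part. It needs only n = 25, five methods, complete rankings and an assumed 5% level. If independent-groups tests are used, the false-positive rate roughly doubles, to about 10% to 11%. The loss of power on times is sound in direction when times within a subject are positively correlated, but its size depends on the assumptions in part C. How far ease departs from preference cannot be quantified from the documents.

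The change should be made before data collection, because a preference not recorded before home use cannot be recovered later under the same conditions.

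**What to change.** 1. **Visit 2.** After the last method and before lenses go home, record each subject's preference ranking of the five methods in REDCap, and name it as the Aim 1 outcome. Keep the ease ranking as a separate outcome.

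2. **Data Collection and Analysis.** For comparing methods on ranks, replace Kruskal-Wallis with Friedman. For times, specify repeated-measures ANOVA, or a mixed model with subject, method and order terms. The mixed model uses the randomized order and can include subjects who leave a method untried. Since Friedman needs complete rankings, also say how an untried method enters the ranks.

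3. **First choice.** Report the proportion of subjects ranking each method first, with exact 95% confidence intervals, and test the five proportions with an exact goodness-of-fit test. As a guide to precision, 5 of 25 has an exact interval of about 7% to 41%.

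**Cost.** One extra item at an existing visit and a few sentences of text, with no added subjects or visits. The main drawback is that some subjects may simply copy their ease order into the preference ranking.

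### Aim 2 covers applying and removing lenses, but Hypothesis 2 and the planned regression most naturally cover application only, so no factor for removal time is tested

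*Combined protocol and SAP*

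**What the plan says.** - **Goal (Introduction & Rationale).** Besides the best application method, the study is to learn "factors associated with successfully completing SL application and removal training".
- **Aim 2 (Specific Aims).** The question is what affects how long a new wearer needs "to be able to successfully apply and remove their SLs".
- **Hypothesis 2 (Specific Aims).** Four factors (past contact lens experience, lens diameter, uncorrected acuity and age) "will all influence the total time needed to complete all five application methods successfully". Removal is not mentioned.
- **Data collection (Visit 2: Dispense Visit, step 4).** Removal depends on application: "If a subject is able to apply the lenses, they will be asked to remove the lenses as well". Every removal is done with the same device, a small plunger. On timing, the step says that "the removal time will also be timed for each method (timed separately from application". It also lets a subject give up on a method, or be moved on after 15 minutes, without having applied the lens.
- **Analysis (Data Collection and Analysis).** "Regression analysis will be used to find associations with the speed of being able to complete the application process". ANOVA is planned for comparing application methods, paired t-tests for questionnaire scores, and means and standard deviations for general trends. The word removal does not occur in this section.

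**The concern.** The aim is wider than the outcome chosen to answer it. The goal and Aim 2 join two skills, and the visit procedure times each of them. The hypothesis and the regression then take up only the first. If the plan is followed as written, the trial tests no factor for removal time and so leaves part of its own second aim unanswered, although the data are already being recorded.

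How the gap is closed also matters. The existing outcome is a total over five methods, and someone adding removal later would probably copy that form. Removal differs from application in two ways. It is attempted only after a successful application, so subjects contribute different numbers of removals. It also uses the same device every time, so later removals may be shortened by practice.

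**Working it through.** The plan gives no figure to reproduce here. Subjects and Recruitment says that no true sample size calculation was possible. The main check is to follow removal through the document.

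| Place | Application covered | Removal covered |
|---|---|---|
| Goal, Introduction & Rationale | yes | yes |
| Aim 2, Specific Aims | yes | yes |
| Hypothesis 2, Specific Aims | yes | no |
| Timing, Visit 2 step 4 | yes | yes, recorded separately |
| Regression, Data Collection and Analysis | yes | not named |
| ANOVA, Data Collection and Analysis | yes | not named |

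**Does the regression's outcome include removal?** Three points favour the narrow reading. Hypothesis 2, which the regression serves, names application methods only. Step 4 keeps the two times apart. Step 5 of Visit 2 names both application and removal when it means both, whereas the regression sentence names application alone. If the wide reading is nevertheless intended, the plan does not say how two separately recorded times are to be combined, so an amendment is still needed.

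**Do the planned descriptive statistics fill the gap?** Means and standard deviations could describe removal times. They cannot show which factors influence them, which is what Aim 2 asks.

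**Why a total over methods would be a poor outcome.** Suppose a subject succeeds with k of the 5 methods and each removal takes time t. The total removal time is k × t. Relative to an equally fast subject who succeeds with all five, the ratio is (k × t) / (5 × t) = k/5. For k = 2 this is 2/5 = 40%.

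With assumed times, 2 removals at 60 s give 2 × 60 = 120 s and 5 removals at 30 s give 5 × 30 = 150 s. The slower remover has the smaller total. These times are illustrative only. That the total depends on the number of successes follows from the conditional removal rule in step 4.

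**How large could that distortion be?** It depends on the success rate, for which the documents give no figure. A simulation with 25 subjects shows the range. All its inputs are assumptions:

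- difficulty lowers application success and lengthens each removal, with a log-time slope of 0.15 or 0.25 per SD of difficulty;
- the median removal takes 40 s, with a residual log SD of 0.3;
- practice multiplies successive removal times by 1, 0.85, 0.75, 0.70 and 0.65;
- the logit of success is an intercept minus a slope times difficulty.

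The table gives mean rank correlations of difficulty with each outcome, among subjects with at least one removal. The two values in each cell are for the weaker and stronger removal slope.

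| Assumed success per method (intercept, slope) | With total removal time | With first removal time |
|---|---|---|
| about 75% (1.4, 1.2) | -0.15 / +0.13 | 0.40 / 0.59 |
| about 92% (3.0, 1.2) | 0.37 / 0.63 | 0.43 / 0.60 |
| about 94% (3.0, 0.8) | 0.48 / 0.72 | 0.40 / 0.59 |

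At about 75% success the total loses most of the association. At about 92% the two outcomes perform alike, and at about 94% the total does slightly better.

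**The case against.** **The wording may be loose rather than narrow.** Step 4 describes application and removal within one procedure and calls what the designated eye undergoes the application protocol. Timing the two separately concerns data capture and does not settle what is analysed. This has some force. A reader might infer that the regression sentence cannot include removal; the text does not go that far. The narrow reading is the more natural one, not the only one.

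**Removal is secondary in this study.** The sample of 25 is justified by learning how subjects prefer to apply lenses, the planned abstract is on application methods, and the Conclusions section speaks of evaluating application methods. One removal device is used. This limits how much weight the gap deserves. It does not remove the gap, because the goal and Aim 2 both name removal.

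**The plan never proposes total removal time.** That is correct. A reader might infer that the planned analysis would make the subjects who struggle most look fast, or would reverse the sign of an association. The documents do not support this: no such analysis is planned, and the simulated reversal appears only at the lowest success rate shown, with the weaker removal slope. Retries for up to 15 minutes with encouragement make higher success plausible, though unknown. The dependence on the number of successes is a reason to avoid the sum when adding an analysis; it is not a fault in the present plan.

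**The first-removal outcome has its own limit.** It exists only for subjects who applied a lens successfully, possibly after several failed methods. Counting those without a removal discloses this selection and does not correct it. This stands and must be stated with the result.

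**Conclusion.** The point holds as a mismatch between aim and analysis. Removal is in the goal, in Aim 2 and in the data collected, but Hypothesis 2 does not mention it and the regression most naturally excludes it. As written, no factor for removal time is tested.

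A reader might say that half of Aim 2 goes unanswered. That is not a quantity that the documents support; the exact statement is that the removal component has no hypothesis and no specified analysis of factors.

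The conclusion rests on reading the regression's outcome as application only. On the wider reading, the outcome is undefined rather than absent. No success rate, effect size or simulation is needed for the main point. Those enter only in the advice against summing, where the size of the distortion is unknown because the success rate is unknown.

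The application analyses are unaffected. The gap is worth closing before the data are analysed, and no new data collection is needed.

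**What to change.** Amend Hypothesis 2 and Data Collection and Analysis as follows.

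1. Add an exploratory regression with removal time as its own outcome and the four predictors already named in Hypothesis 2.
2. Define the outcome as the time to the first removal per subject. Alternatively, use all removals in a mixed model with removal number as a covariate and a random effect for subject; this allows for practice and for unequal numbers of removals.
3. Do not sum removal time over methods.
4. Report how many subjects had no removal, and state that the result is conditional on successful application.

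If the sponsor does not want this analysis, restrict the goal and Aim 2 to application. That also restores consistency, but it leaves the recorded removal times without an analysis of factors.

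The cost is a few lines of text and one more regression on data already recorded. The downside is another exploratory four-predictor model on at most 25 subjects, or 25/4 = 6.25 subjects per predictor, and fewer if some never apply a lens. Its estimates will be imprecise and should be labelled as exploratory.
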